6.7.5. Laboratory Data

For non-efficacy laboratory data, a missing baseline value will be replaced with the last available assessment, generally the screening assessment. A retest value will be used if the first test is invalidated, e.g., specimen hemolyzed.

Laboratory data that are continuous in nature but are less than the lower limit of quantitation/limit of detection (LOD) will be, in general, imputed as follows:

- A value that is 1 unit less than the LOD will be used for calculation of descriptive statistics if the data are reported in the form of “ $< x$ ” (x is considered as the LOD). More specifically, $x-1$ is used for data summarization if the data are reported in the form of “ $< x$ ”; and $x.e$ where $e = d-1$, will be used for analysis if the data are reported in the form of “ $< x.d$ ”;
- The LOD will be used for calculation of descriptive statistics if the data is reported in the form of “ $\leq x$ ” or “ $\geq x$ ”.

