4.3. Sample Size Considerations

The sample size of up to approximately 24 subjects in this study is based on an estimate of the number of subjects who may enroll either after completing Study SPR001-201 or as SPR001-naïve subjects. There is no statistical basis for the sample size,

The final sample size for the study is n=11.

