6.7. Handling of Missing Data

6.7.1. Missing Efficacy Endpoints

Missing data will not be imputed for continuous efficacy endpoints in primary or secondary analyses.

A sensitivity analysis will impute missing hormone data using last observation carried forward.

For binary efficacy endpoints, missing data will be assumed as a failure (subject did not meet the efficacy endpoint).

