9.5. Analysis of Secondary Efficacy Endpoints

Analysis of hormone data will be conducted only on subgroups.

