9.5.1. Efficacy Analysis of Hormones

Hormones [17-OHP; ACTH; A4; Testosterone] will be summarized using geometric means and geometric means ratios to assess change and percentage change.

A summary of [17-OHP; ACTH; A4; Testosterone] by Visit will include the observed parameter (using GM reporting format).

Figures

A serial figure with week as the x-axis and % change as the y-axis will be provided.

Separate serial figures will be provided for each hormone.

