11. APPENDICES

11.1. Reporting Formats

C: Continuous endpoints will be presented with an 8-point summary using the following reporting structure, unless otherwise noted,

N	x
Mean (SD)	x.xx (x.xxxx)
Median	x
Q1, Q3	xx.x, xx.x
Minimum, Maximum	xx.x, xx.x

GM: Continuous endpoints reported in log scale with a Geometric mean

n	x
Geometric Mean (CV)	x.xx (x.xxxx)
95 CI for Geometric mean	x.xx, x.xx
95 CI for Geometric mean Ratio (GMR)	x.xx
95 CI for GMR	x.xx, x.xx

Percentage Change from Baseline	0.xx
95% CI for Percentage Change	x.xx, x.xx

F: Frequency endpoints will be presented by a 3-point summary using the following reporting structure, unless otherwise noted,

Count (%)	x (xx.x)
-----------	----------

MF Categorical variables (multiple frequency) will be presented by a 3-point summary using the following reporting structure, unless otherwise noted, where the sum of the category n's is the total n

n	x
Category 1 count (%)	x (x.x)
Category 2 count (%)	x (x.x)

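### The below-LOD rule (limit minus one unit) does not suit the log-scale hormone summaries: for some printed limits it imputes zero, and otherwise the value depends on reporting units

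*SAP*

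**What the plan says.** The second part of SAP 6.7.5 sets the rule for results under the assay limit: "Laboratory data that are continuous in nature but are less than the lower limit of quantitation/limit of detection (LOD) will be, in general, imputed". The method is subtraction: "A value that is 1 unit less than the LOD will be used for calculation of descriptive statistics". For a limit printed as a whole number, one is taken off. For a limit printed with a decimal, the decimal digit is lowered by one.

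SAP 9.5.1 states that 17-OHP, ACTH, androstenedione (A4) and testosterone "will be summarized using geometric means and geometric means ratios to assess change and percentage change". The format in SAP 11.1 is defined as "GM: Continuous endpoints reported in log scale with a Geometric mean". SAP 7.8 uses it for baseline 17-OHP, ACTH and A4 as well.

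SAP 6.7.1 covers missing hormone values ("Missing data will not be imputed for continuous efficacy endpoints in primary or secondary analyses", with last observation carried forward as a sensitivity analysis). It does not mention values below the LOD. Neither document gives an assay limit for any hormone or a rule for zeros on the log scale.

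**The concern.** Subtracting one unit is workable for arithmetic means, where a zero does no harm. On the log scale a zero has no logarithm, and the plan does not say what happens next. The programmer would have to choose between a geometric mean of zero, an error, an exclusion or an unplanned substitute. That choice would be made with the data in view.

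The drug is meant to lower these hormones, so on-treatment values move towards the assay limit. The groups are also very small. SAP 4.3 says "The final sample size for the study is n=11", and SAP 9.5 adds "Analysis of hormone data will be conducted only on subgroups". In a group of a few subjects, the handling of one value can decide the reported percentage change.

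**Working it through.** The plan states no figure to reproduce. The check applies the rule to example limits and follows the result through a geometric mean ratio.

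**1. What the rule yields.** Suppose the printed limit equals k units in its last reported place. One unit less is then (k − 1)/k of the LOD.

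| Printed | k | Imputed | Share of LOD | Log |
|---|---|---|---|---|
| `<1` | 1 | 0 | 0% | undefined |
| `<0.1` | 1 | 0.0 | 0% | undefined |
| `<0.01` | 1 | 0.00 | 0% | undefined |
| `<2` | 2 | 1 | 50% | defined |
| `<5` | 5 | 4 | 80% | defined |
| `<10` | 10 | 9 | 90% | defined |
| `<5.0` | 50 | 4.9 | 98% | defined |

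For `<5.0`, the digit formula taken literally asks for a last digit of 0 − 1 = −1. The value 4.9 comes from reading the rule as one unit in the last place. Zero arises only when k = 1.

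**2. Dependence on units.** Take one physical limit, 10 ng/dL (assumed). Printed as `<10` ng/dL it becomes 9 ng/dL. Printed as `<0.1` ng/mL it becomes 0, and as `<0.10` ng/mL it becomes 9 ng/dL. Printed as `<100` pg/mL it becomes 99 pg/mL, which is 9.9 ng/dL.

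**3. Effect when the value stays positive.** The geometric mean ratio is exp(mean of the log ratios). Assume one subject falls from 200 ng/dL to below 10 ng/dL and all others have ratio 0.60.

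- n = 11, imputed 9: 0.60^(10/11) × (9/200)^(1/11) = 0.474, a change of −52.6%. With 9.9 it is −52.2%.
- n = 4, imputed 9: 0.60^(3/4) × (9/200)^(1/4) = 0.314, a change of −68.6%. With 9.9 it is −67.8%.

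The gap is 0.4 and 0.8 percentage points. In general a positive imputed value lies between 50% and 100% of the LOD. For one affected subject, the printing format can therefore move the ratio by at most a factor of 2^(1/n): 1.065 at n = 11 and 1.189 at n = 4.

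**4. Effect if a zero were excluded.** Assume a limit printed as `<1`, one subject falling from 50 units to below it, and all others at ratio 0.60.

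- Excluded: −40.0% at any n.
- Kept at LOD/2 = 0.5, n = 11: 0.60^(10/11) × (0.5/50)^(1/11) = 0.414, a change of −58.6%.
- Kept at LOD/2 = 0.5, n = 4: 0.60^(3/4) × (0.5/50)^(1/4) = 0.216, a change of −78.4%.

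**5. Group sizes.** The tables for 17-OHP, ACTH and A4 in SAP 11.3 use three disjoint groups: dexamethasone, non-dexamethasone with severe/moderate control issues, and non-dexamethasone with mild control issues. Since 11/3 = 3.67, at least one of them holds 3 subjects or fewer.

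**The case against.** **Scope.** SAP 3.2.2 calls the hormones biomarkers, Table 2 gives biomarkers a row separate from laboratory data, and SAP 8.4 describes routine laboratory data as hematology, chemistry and urinalysis. Section 6.7.5 might therefore not govern hormones. Against this, the only restriction in that section is in another sentence ("For non-efficacy laboratory data, a missing baseline value will be replaced with the last available assessment"), and the below-LOD paragraph carries none. If hormones were outside it, they would have no below-LOD rule at all, and the same sentence would be needed.

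**Likelihood.** SAP 6.6.3 gives targets of 1200 ng/dL for 17-OHP, 63.3 pg/mL for ACTH, and 152 (males) and 262 (females) ng/dL for A4. In those units, a zero from `<1` needs a very low result. A fall in 17-OHP from the screening threshold of 800 ng/dL to below 1 exceeds 1 − 1/800 = 99.8%. That threshold applies to naïve subjects and to those rolling over more than 3 months after their last visit in the earlier study. This part of the objection stands, and the trigger is narrow. Testosterone, whose unit is not stated, and subjects with low baselines are less clear.

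**Stronger readings.** A reader might infer that the largest reductions would drop out. The SAP nowhere says that zeros are excluded. Moreover, a value below the LOD is a low level and not necessarily a large fall: a subject with a low baseline can cross the limit with a modest change, and a below-LOD baseline is not a strong response. A reader might also build an example of five subjects, four at ratio 0.80 and one at 0.05. Excluding the last gives a 20% reduction, while keeping it gives 1 − 0.80^(4/5) × 0.05^(1/5) = 54%. This works only with a limit that produces zero and a low baseline, since a ratio of 0.05 ending below 1 unit needs a baseline below 20 units. Severe/moderate subjects have ACTH above 2 × 63.3 = 126.6 pg/mL, and 5% of that is above 6.3. Their A4 exceeds 304 (males) or 524 (females) ng/dL, and 5% of that is above 15 or 26. None of these reaches a `<1` limit.

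**Safeguards.** The rule applies only in general, SAP 2 provides for changes identified in the study report, and Listing 16.2.6.1 shows individual post-baseline hormone values. A failure would thus probably be noticed, but its remedy would be chosen after the data were seen.

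**Conclusion.** The concern holds as a conditional defect of minor weight. For any limit printed as one unit in its last place, the stated rule cannot produce the stated statistic, and no other section resolves the conflict. For all other limits the summary can be computed. The substitute then varies with how the laboratory prints its limit, usually to small effect (under one percentage point in step 3).

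Frequency is unknown because no assay limits are given, so every numerical example here rests on assumed limits and baselines. If on-treatment zeros were excluded, the reduction would tend to be understated: by about 19 points with 11 subjects and 38 with 4 under the assumptions of step 4. If the zero were treated as missing, the carried-forward sensitivity analysis could also put an earlier measurable value in its place. These are secondary endpoints with nominal p-values in a study that SAP 9.4 describes as hypothesis generating, which keeps the weight low.

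**What to change.** Add one sentence to SAP 6.7.5, with a cross-reference in 9.5.1. For 17-OHP, ACTH, A4, testosterone and any other summary on the log scale, replace a result below the LOD by a fixed positive fraction of the LOD, for example LOD/2, whatever units or decimals the laboratory reports. Report the number of such results at baseline and at each visit.

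The cost is a line of text, a line of code and a count in each table. The downside is that LOD/2 is itself a convention. In the example of step 3, LOD/√2 instead of LOD/2 gives −53.6% against −55.1% at n = 11, and −70.4% against −72.9% at n = 4. The reported counts show readers where that choice could matter.

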7. STUDY POPULATION

7.1. Enrollment by Investigator

Enrollment by investigator will summarize the number of subjects enrolled by investigator by treatment group and total, sorted by highest enroller first.

The randomized analysis set is used to for this summary.

7.2. Subjects Disposition

Subject disposition information will be summarized for all subjects by dose. Summaries will include:

Label	Reporting Format
Subject Enrolled	F
Subjects Enrolled and Treated with Study Drug	F
Subjects Enrolled and NOT Treated with Study Drug	F
Subjects Completing Study	F
Subjects Not Completing Study	MF; Adverse event, Lost of follow-up, Non-compliance with study drug, Physician Decision, Pregnancy, Protocol Violation, Study terminated by Sponsor, Other

A listing of subject disposition will include the ITT analysis set status, the date of informed consent signed, the date of first dose and last dose of study drug, primary reason for subject discontinuation of study medication, the date of last visit, study completion status, primary reason for study termination, and the date of last contact.

The randomized analysis set is used to for this summary.

7.3. Protocol Deviations

A summary of protocol deviation identified prior to database lock by site will be provided.

In addition, 2 listings will be provided, a listing of protocol deviation identified prior to database lock and a listing of protocol deviation identified post database lock. The second listing will compose any new protocols derivations identified during site close out visits.

In addition, a listing of all major analysis protocol deviations will be provided.

The randomized analysis set is used to for this summary.

7.4. Demographic and Baseline Characteristics

Demographics and baseline characteristics will be summarized.

Label	Reporting Format
Subject Age	C
Sex	MF; Male, Female, Missing
Ethnicity	MF; Hispanic or Latino, Not Hispanic or Latino, Not Reported, Unknown, Missing
Race	MF; White, Black or African American, Asian, American Indian or Alaska Native, Native Hawaiian or Other Pacific Islander, Other, Multiple Race, Missing
Baseline Weight (kg)	C
Baseline Height (cm)	C
BMI (kg/m ²)	C

A listing will also be provided.

7.5. Listing of Subject Inclusion and Exclusion Criteria

A listing of Inclusion and Exclusion criteria will be provided.

7.6. Medical History and Medical Conditions Present at Entry

Medical history will be summarized by treatment group, system Organ class and preferred term.

7.7. Prior Medication History and Medications Present at Entry

Prior Medications will be listed and summarized separately.

Summaries will be provided for glucocorticoid medications and prior medications summarizing medication name by the number and proportions of subjects with use.

Coding logic for each group is in Appendix Section [11.2](#).

7.8. Baseline Clinical Characteristics

A summary of Baseline Hormones will be provided:

Label	Reporting Format
Baseline Serum 17-OHP	GM
Baseline ACTH	GM
Baseline Androstenedione (A4)	GM

7.9. Mini International Neuropsychiatric Interview

The number and percent of subjects answering affirmatively (i.e., “yes”) to the questions in the Mini International Neuropsychiatric Interview (MINI) (version 7.0.2) questionnaire will be tabulated by individual cohort and overall.

The topics of the questionnaire include past and current instances of Major Depressive Episode, Suicidality, Manic/Hypomanic Episodes, Bipolar I and II Disorders, and Psychotic Disorders (including Major Depressive Episodes or Bipolar Episodes with Psychotic Features).

8. SAFETY AND TOLERABILITY

The analysis of safety and tolerability data includes an overall summary of tolerability, adverse event preferred terms by body/organ system, drug exposure (duration of treatment), dosing information/compliance, concomitant medications, clinical laboratory results, vital signs and ECGs. Tables summarizing the adverse events reported by subjects who died, experienced non-fatal serious adverse events (SAE), or prematurely discontinued the study due to adverse event (AEs) will be prepared. Summaries of potentially clinically notable laboratory results and vital sign abnormalities are presented.

In general, inferential statistical tests are not performed for adverse event incidence rates.

For all safety analyses, the safety analysis population will be used.

8.1. Adverse Event Preferred Term and Body/Organ System Summary Tables

Adverse events will be coded to the preferred terms of the Medical Dictionary for Regulatory Activities (MedDRA®). Summaries will present by system organ class (SOC), preferred term (PT) and severity and/or relatedness, the frequency and percentage of subjects reporting each observed event.

A treatment-emergent adverse event (TEAE) will be defined as any AE that begins on or after the date of first dose of study drug up to the date of last dose of study drug plus the number of days in the follow-up period. AEs observed during the period from obtaining informed consent to the start of administration of study drug will be regarded separately from TEAEs.

All AEs and all TEAEs will be listed by subject.

Subjects who experienced treatment-limiting AEs will be listed. Treatment-limiting AEs are defined as any event that leads to permanent or temporary discontinuation from treatment, or a reduction in the treatment dose.

Summary of adverse events will be dependent on adverse events observed. If no adverse events meeting a specific table are observed, the summary table will not be completed. Blank summary tables will not be utilized.

The following is the list of adverse event tables:

Overall:

- Overall Summary of Adverse Events

Label	Reporting Format
Adverse Event	F
Moderate or Severe Adverse Event	F
Adverse Event Related to Study Drug	F
Moderate or Severe Adverse Event Related to Study Drug	F
Serious Adverse Event	F
Serious Adverse Event Related to Study Drug	F
Adverse Events Leading to Permanent Study Drug Discontinuation	F
Adverse Events Leading to Temporary Interruption of Study Drug	F
Death During Study	F

By preferred term:

- Treatment-emergent Adverse Events by PT
- Treatment-emergent Adverse Events by SOC and PT

By severity:

- Treatment-emergent Adverse Events by SOC, PT and Severity
- Serious Adverse Events
- Deaths during Study

By relatedness:

- Drug-Related Treatment-emergent Adverse Events by SOC and PT
- Drug-Related Treatment-emergent Adverse Events by SOC, PT and Severity
- Drug-related Serious Adverse Events

Other:

- Adverse events leading to premature study drug discontinuation

8.2. Total Duration of Therapy and Compliance

Study drug exposure (Number of doses) will be summarized using the 8-point descriptive summary. The source for exposure data is the drug accountability data domain.

Study drug compliance will be assessed using the following categories using the same source as the drug exposure data:

Label	Reporting Format
≥100%;	F
95%;	F
90%;	F
80%;	F

Study drug administration (date/time and study day) will be provided in a data listing. The source for study drug administration is the diary data domain.

8.3. Concomitant and Other Medications

Concomitant medications, prescribed and over the counter, that the subject takes or continues to take after the baseline visit will be summarized according to the following rules.

Medications with a start date before the date of the first dose of study medication will also appear in the prior medication summary table. The same summary format applies here as it was described for the medication history and medications present at study entry tables with respect to major drug class, minor drug class, and generic name. The data will be presented by treatment group and for all treated subjects. The same subject counting procedures will also apply (e.g.,

major class frequencies will represent subjects only once even though the same subject can be counted for multiple minor sub-classes and generic names).

The supportive individual subject data listing should be organized as the medication history listings with trade and generic drug names, start and stop dates, days relative to the start of therapy, dose, frequency, route, and indication(s).

8.4. Routine Laboratory Data

Laboratory data, hematology, serum chemistry and urinalysis, will be summarized in terms of observed values, changes from baseline for each period. In addition, changes from baseline for each period relative to normal ranges (e.g., shifts from normal to abnormal high/low) will be summarized in hematology: shift from baseline, serum chemistry: shift from baseline and urinalysis: shift from baseline.

Listings will flag laboratory values that are outside of normal range.

A listing of all abnormal lab values will be provided.

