physical examination may exclude rectal, genitourinary, and breast exams. An abbreviated physical examination will be conducted at Weeks 4 and 8 and final follow-up. Height needs to be collected at screening only. As part of the examination of the skin, acne will be evaluated for all subjects using an IGA score at baseline and Weeks 4, 8, and 12; hirsutism will be evaluated for female subjects using an mFG score at baseline and Week 12. Female subjects will be asked about their last menstrual period as part of both full and abbreviated physical exams.

 For SPR001-naïve male subjects, a scrotal ultrasound will be conducted at the initial screening visit. For SPR001-experienced male subjects rolling over from Study SPR001-201, a scrotal ultrasound will be conducted at the initial screening visit only if the subject has not had a prior scrotal ultrasound within 3 months before screening. For all male subjects, if the prior or screening scrotal ultrasound reveals no evidence of TART, the scrotal ultrasound need not be repeated at either Day 1 or Week 12. If the prior or screening scrotal ultrasound does show evidence of TART(s), the scrotal ultrasound will be repeated at Day 1 and Week 12.

 All male subjects should be encouraged (though not required) to provide a semen sample. Semen will be collected from male subjects for analysis of sperm count, morphology, and motility.

 Female subjects will record menstrual information (including start and stop dates of menses and whether the flow was light, moderate, or heavy) in a menstrual diary throughout the 12-week screening period and the 12-week treatment period. A menstrual diary will be handed out at the screening visit and collected at the Day 1 visit, and a second menstrual diary will be handed out at the Day 1 visit and collected at the Week 12 visit.

 The 4-week SF-36 will be administered.

 Subjects will be dispensed a 4-week supply of study drug each time. If a morning dose of study drug is added, subjects should hold off on taking their morning dose of study drug on the mornings of all study visits until after laboratory assessments have been completed. On all other days during the study, subjects should take their morning dose of study drug (if applicable) at the usual time.

	Screening Period	Treatment Period								Follow-up/ET
		1  Screening	2 Baseline	3	4	5	6	7	8	
VISIT NUMBER										9
STUDY WEEK		0	2	4	6	8	10	12	16	

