### 2.3.3 Assessment of Potential Risks and Benefits

Multiple study design elements have been incorporated to mitigate the potential risks of LFT laboratory abnormalities, testicular injury, and thyroid effects described in [Section 2.3.1](#). Because these risks are all associated with higher doses of SPR001, study drug will initially be administered in this study at 400 mg QD, which is within the range of clinical precedence that has been safe and well tolerated. Additionally, clinical laboratory measures of liver chemistry, testicular function, and thyroid function will be assessed every 2 weeks throughout the treatment period of this study. Liver chemistry will be monitored by measuring ALT, aspartate aminotransferase (AST), alkaline phosphatase (ALP), gamma-glutamyltransferase (GGT), and total and direct bilirubin. Testicular function will be monitored by measuring LH, FSH, inhibin B, and SHBG; performing scrotal ultrasounds; and conducting semen analysis. Thyroid function will be monitored via a thyroid panel that measures T3, T4, and thyroid-stimulating hormone (TSH). Finally, strict individual treatment stopping criteria for liver chemistry findings and a criterion for increased liver chemistry monitoring are in place (see [Section 7.2.1](#) and [Section 12.2](#)).

The mild and reversible toxicologic effects of SPR001 on the male reproductive tract in nonclinical studies occurred in the context of animals with normal, rather than elevated, baseline hormone function. As a CRF1 receptor antagonist, SPR001 is intended to reduce abnormally elevated ACTH and androgen levels. In nonclinical models where baseline hormone levels are within normal ranges, clinical benefits are not expected, and indeed, toxicities may be expected as a result of androgen reduction outside of the normal range. However, in patients with CAH, whose baseline ACTH and androgen levels are pathologically elevated, androgen reduction would be considered a positive, therapeutic effect.

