⁷ Subjects should be on a stable regimen of glucocorticoid replacement for a minimum of 30 days before baseline and throughout the treatment period. On the mornings of all study visits, including screening, subjects should hold off on taking any morning glucocorticoid medication until after laboratory assessments have been completed. On all other days during the study, subjects may take any morning dose of glucocorticoid medication at their usual time.

VISIT NUMBER	Screening Period		Treatment Period							Follow-up/ET
	1 ¹ Screening	2 Baseline	3	4	5	6	7	8	9	
STUDY WEEK		0	2	4	6	8	10	12	16	
STUDY DAY ²	≤30 days before Day 1	1	15	29	43	57	71	85		Last dose +30 days
Site Visits ³	X	X		X		X		X		X
Home Visits ⁴			X		X		X			
Clinical laboratory ^{8,9}	X	X	X	X	X	X	X	X		X
HbA1c ⁸			X		X		X			X
Key hormones ^{8,10}	X	X	X	X	X	X	X	X		X
Exploratory adrenal hormones ^{8,11}			X		X		X			X
PK ^{8,12}	X	X		X		X		X		X
Hepatitis B & C and HIV screening ¹³	X									
eGFR for screening ^{13,14}	X									
Pregnancy test for WOCP ¹⁵	X	X		X		X		X		X
Vital signs ¹⁶ and body weight	X	X	X	X	X	X	X	X		X

⁸ Samples for these lab assessments will be obtained at the beginning of each study visit (8am), after overnight fast (nothing to eat since the previous midnight), and before the subject has taken any morning dose of glucocorticoid medication. If a morning dose of study drug is added, samples for these lab assessments will be obtained before the morning dose of study drug for that day (where applicable).

⁹ Clinical laboratory assessments include hematology, clinical chemistry, fasting glucose, lipid panel, thyroid panel, urinalysis, LH, FSH, inhibin B, SHBG, renin, aldosterone, and, for females only, estradiol, prolactin, and progesterone.

¹⁰ ACTH, 17-OHP, androstenedione, testosterone, and background glucocorticoid levels (cortisol/prednisolone/dexamethasone, depending on what the subject is taking) will be measured from blood samples. 17-OHP will also be measured from a saliva sample.

¹¹ A single blood sample will be drawn for measurement of exploratory adrenal hormones at each specified visit.

¹² A single blood sample will be drawn for PK measurement at each specified visit. The PK blood sample does not need to be obtained from SPR001-naïve subjects at screening.

¹³ These screening assessments will be performed for SPR001-naïve subjects and for subjects who completed the final follow-up visit in Study SPR001-201 >3 months before the screening visit for this study.

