5. PLANNED ANALYSES

5.1.1. Changes to Protocol Specified Analyses

Due to the low enrollment numbers for subjects enriched with acne and hirsutism at baseline (n=2), these endpoints will not be summarized.

Due to no samples collected, analysis of semen will not be summarized.

Due to the study short duration and lack of adequate baseline data, menstrual cyclicity will not be summarized.

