9.6.3. Changes in Insulin profile

The following parameters will be repeated from the standard lab output and as a standalone summary, changes in insulin profile summary by visit:

- Hemoglobin A1C
- Glucose

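### The SAP specifies no summary or listing for the thyroid panel or for LH, FSH, inhibin B and SHBG, the laboratory markers the protocol chose for two of its three named risks

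*SAP*

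**What the plan says.** Protocol 2.3.3 says that design elements were added to mitigate "the potential risks of LFT laboratory abnormalities, testicular injury, and thyroid effects", and that "clinical laboratory measures of liver chemistry, testicular function, and thyroid function will be assessed every 2 weeks throughout the treatment period of this study". For the testis: "Testicular function will be monitored by measuring LH, FSH, inhibin B, and SHBG; performing scrotal ultrasounds; and conducting semen analysis". For the thyroid it names T3, T4 and TSH. Protocol 3 places change in clinical laboratory values among the primary endpoints. Protocol 9.3.5 commits to listing and descriptively summarizing clinical laboratory values and excepts no panel.

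The SAP keeps the same scope when it defines what is collected. Footnote 9 to the schedule in SAP 4.5 counts as clinical laboratory not only hematology and chemistry but also "thyroid panel, urinalysis, LH, FSH, inhibin B, SHBG, renin, aldosterone".

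The analysis text is narrower. SAP 8.4 reads: "Laboratory data, hematology, serum chemistry and urinalysis, will be summarized in terms of observed values, changes from baseline for each period". It adds shift summaries for the same three panels and a listing of abnormal values. SAP 5.1.1 declares three departures from the protocol: acne and hirsutism, menstrual cyclicity, and semen ("Due to no samples collected, analysis of semen will not be summarized"). It mentions neither the thyroid panel nor the reproductive hormones.

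**The concern.** The protocol argues that 12 weeks of dosing is acceptable partly because specific markers will be watched for specific risks. Protocol 4.2 bases the treatment length on the 3-month toxicology studies. At their top dose, those studies showed testicular findings in rats and dogs and thyroid findings in dogs (Protocol 2.2.3 and 2.3.1). Protocol 2.3.1 adds that thyroid function was not evaluated in Phase 1.

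A programmer who follows SAP 8.4 and 11.3 literally would produce liver results within serum chemistry and nothing for the markers of the other two risks. The study report would then depart from Protocol 9.3.5 on part of a primary endpoint, with no record that anyone decided to do so.

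**Working it through.** The plan states no figure on this point, so there is none to reproduce. The check compares markers with planned outputs.

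**Step 1: markers against outputs**

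| Risk (Protocol 2.3.3) | Marker | Planned output in the SAP |
|---|---|---|
| Liver | ALT, AST, ALP, GGT, bilirubin | Serum chemistry tables, if read with the Clinical Chemistry row of Protocol 12.4 |
| Testis | LH, FSH, inhibin B, SHBG | None named |
| Testis | Semen | Declared dropped (SAP 5.1.1) |
| Testis | Scrotal ultrasound | SAP 8.9 text, only for men with testicular adrenal rest tumors (TARTs) at baseline; no table in 11.3 |
| Thyroid | T3, T4, TSH | None named |

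Protocol 12.4 puts the thyroid panel in its own row and the four reproductive markers under other tests, both outside clinical chemistry.

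**Step 2: count in SAP 11.3**

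- Laboratory tables: hematology 2, serum chemistry 2, urinalysis 1, so 5. Tables naming any of the seven markers: 0.
- Laboratory listings: hematology 9, chemistry 4, abnormal findings 2 (chemistry and hematology), so 15. Listings naming any of the seven: 0.
- The baseline table in SAP 6.5 also describes laboratory data as chemistry, hematology and urinalysis. The restriction therefore does not appear only in the index.

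**Step 3: could another output carry them?**

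Listing 16.2.6.1 (post-baseline hormones) is not itemized. Its natural partner is the baseline hormone summary in SAP 7.8, which holds 17-OHP, ACTH and androstenedione. Testosterone is tabulated overall and by sex (14.2.4.1 to 14.2.4.3), as a secondary efficacy endpoint.

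**Step 4: amount of data affected**

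Clinical laboratory samples are scheduled at baseline, 6 on-treatment visits and follow-up. SAP 4.3 gives a final n of 11. If every subject attends every visit:

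- thyroid: 11 × 7 post-baseline visits × 3 tests = 231 changes from baseline
- reproductive: 11 × 7 × 4 = 308
- total: 231 + 308 = 539

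This is a ceiling, because missed visits reduce it.

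**Step 5: what added tables could show**

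After zero events in n subjects, the exact one-sided 95% upper limit is 1 − 0.05^(1/n). For n = 11 this is 23.8%; the upper end of the two-sided 95% interval, 1 − 0.025^(1/n), is 28.5%. The number of men is not given. If it is assumed to be 4 to 8, the one-sided limit runs from 53% down to 31%.

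**Step 6: secondary items**

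Protocol 9.3.6 says fasting insulin and the exploratory adrenal hormones will be summarized. SAP 9.6.3 promises "changes in insulin profile summary by visit" but lists only HbA1c and glucose. SAP 3.1.3 keeps the exploratory adrenal hormones as an objective, while 3.2.3 and 11.3 give them no endpoint or table.

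**The case against.** A reader might infer that the trial cannot answer its primary safety question for testis and thyroid. The documents do not support that. The samples are scheduled every 2 weeks, the protocol's commitment to summarize stands, and SAP 11.3 says its index may be updated after finalization. The primary objective is also safety in general and does not single out these organs.

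It is also too strong to say that no reproductive hormone is tabulated, or that a man without a TART has no post-baseline testicular measure in any output. Testosterone in males has its own table. The ultrasound schedules differ as well. On the Day 1 and end-of-treatment scans, Protocol 1.3, footnote 18, says "if the prior or screening scrotal ultrasound reveals no evidence of TART, the scrotal ultrasound need not be repeated at either Day 1 or Week" (the end-of-treatment visit), which is permissive. The SAP 4.5 schedule marks later scans with no TART condition, and SAP 8.9 speaks of selected men.

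Three further points are fair.

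- **Serum chemistry is not itemized in the SAP.** SAP 9.6.2 and 9.6.3 draw lipids and HbA1c from the standard laboratory output, although neither is in the protocol's chemistry row. The missing tests might be produced there too. This stands as a reason to say not specified rather than never tabulated. Lipids and HbA1c are at least named in an analysis section; the seven markers are not.
- **Adverse event tables and a listing of abnormal values remain.** This stands, but neither shows drift within the normal range. Protocol 8.1.5 also treats disease-associated findings as not clinically significant unless more severe than expected, and Protocol 7.2.6 expects abnormal androgens and progestogens at baseline.
- **The FSH value in Protocol 12.3.2 is investigator guidance.** Protocol 7.2.7 says so, and the SAP is not obliged to apply it. This stands.

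Testosterone is a weak substitute. Protocol 2.3.3 regards androgen reduction in these patients as therapeutic, so a fall cannot separate efficacy from testicular harm.

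**Conclusion.** The point holds as a specification gap. For two of three named risks, none of the seven chosen laboratory markers is named in a planned table or listing, and the departure from Protocol 9.3.5 is undeclared. The remaining testicular evidence is thin: no semen was collected, and the ultrasound summary is limited to men with TARTs at baseline and has no table.

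This should be fixed, but it is not a failure of the primary objective. The data are collected and the gap closes without new samples. The conclusion assumes that serum chemistry means roughly what Protocol 12.4 calls clinical chemistry, and that no programming specification outside these documents adds the tests. The firmer limit on any safety conclusion, for the liver as well, is 11 subjects with no control arm. The added tables would describe trends and could not rule out an event rate of about one in five.

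The insulin and exploratory adrenal hormone omissions are real but secondary. Protocol 8.5.3 describes the adrenal samples as stored, with an optional analyte list, and the SAP 4.5 schedule row names HbA1c without insulin. Whether these assays were run is unclear.

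**What to change.** In SAP 8.4 and 11.3:

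- Add by-visit tables of observed values and change from baseline, with by-subject listings, for T3, T4 and TSH in all subjects and for LH, FSH, inhibin B and SHBG by sex.
- Extend the abnormal-value listing to these seven tests.
- Add the ultrasound table that SAP 8.9 describes, and reconcile which men are rescanned under the two schedules.

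Alternatively, declare and justify the omission in SAP 5.1.1.

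Shift tables are optional, since Protocol 9.3.5 only says they may be used. A count against the FSH guidance value is also optional.

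For fasting insulin and the exploratory adrenal hormones, add the summaries or record in 5.1.1 that they were dropped and why.

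The cost is a few sentences of SAP text and a small set of tables and listings in formats already planned for chemistry. No new samples are needed.
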